The Role of Trimetazidine on Right Ventricle Function in
Pulmonary Arterial Hypertension in National
Cardiovascular Center Harapan Kita Hospital
(TRIMETA-PH)

STUDY PROTOCOL AND STATISTICAL ANALYSIS

NCT: 03273387

STUDY DATES: SEPTEMBER 10th 2017

**DEPARTMENT OF CARDIOLOGY AND VASCULAR MEDICINE
FACULTY OF MEDICINE UNIVERSITAS INDONESIA
NATIONAL CARDIOVASCULAR CENTER HARAPAN KITA HOSPITAL**

This study is a single centre, randomized, double-blind, placebo-controlled, proof of concept study of trimetazidine effect in RV function of PAH patients. The study protocol was approved by the institutional review board in National Cardiovascular Center Harapan Kita Hospital Universitas Indonesia (NCCHK-UI). The member of committee were involved in the study design, protocol review, and guidance throughout the study conduct. All patients gave written informed consent.

Study Population

Patients which eligible for the study were recruited from (NCCHK-UI) PAH outpatient clinic. Patients were selected based on following inclusion and exclusion criteria. Inclusion criteria including age 18-65 years old, presence of precapillary pulmonary hypertension $mPAP \geq 25$ mmHg with left ventricle end diastolic pressure (LVEDP) or mean left atrial pressure (mLAP) ≤ 15 mmHg, WHO functional class II or III, evidence of RV dysfunction with RVEF $< 45\%$ according to cardiovascular magnetic resonance imaging (CMR), and stable dose of pulmonary vasodilator therapy in the 4 weeks before randomization.

Exclusion criteria including LVEDP or mLAP > 15 mmHg, WHO functional class IV, pregnancy or lactation, severe renal dysfunction with estimated glomerular filtration < 30 ml/min/1.73 m² or routine hemodialysis, presenting malignant arrhythmia, left ventricular ejection fraction (LVEF) $< 50\%$, claustrophobia, and Parkinson disease.

Study Protocol

Patients who met the following inclusion and exclusion criteria will be randomized in 1:1 ratio to receive twice-daily 35 mg trimetazidine or twice-daily placebo on top of their standard PAH regime for 3 months. Study procedure included cardiac catheterization at baseline, physical examination, SF-36 functional capacity questionnaire, and CMR examination at baseline and after 3 month treatment. Follow-up visits will be recorded during annual PAH outpatient visit at months 1,2, and 3. Adherence to study medication was encourage throughout study period including phone call reminder and pill counts during annual outpatient visit. All adverse event were recorded, including major adverse cardiovascular event (MACE) which defined as severe deterioration of health resulting in death, risk of death, hospitalization, or disability.

Participants required right heart catheterization to evaluate the eligibility. Right heart and pulmonary artery catheterization was performed from the right femoral vein approach. Multipurpose (MP) catheter was used to record mPAP (MP 90cm, Mach1™, Boston Scientific). Left heart catheterization was performed from right femoral artery using pigtail 6F catheter to record LVEDP (pigtail6F, Boston Scientific). In the case of PAH due to congenital heart disease with left to right shunt, we measured mLAP using MP catheter directly from the appropriate shunt. Pressure recordings were analyzed using Siemens Axiom Sensis XP.

Participants underwent CMR (Phillips Achieva 1.5 Tesla) examination at baseline and after 3 months treatment to assess RVEF, LVEF, LV and RV end diastolic volume (RVEDV and LVEDV0, RV and LV end systolic volume (RVESV and LVESV), and fibrosis using native T1 mapping. General RV and LV structure and function protocol

were conducted according to SMCR guideline 2013. Cardiac fibrosis analysis was performed using Look Locker imaging protocol. All CMR analysis was done using circle CVI42 version 5.9 software (Circle Cardiovascular imaging inc. Canada).

Functional class was assessed during monthly visit according to WHO. Their functional status was calculated using short form health survey (SF-36) questionnaire which was recorded at baseline and after 3 months treatment.

Study Outcomes

The primary outcome was the differences of RVEF after 3 months therapy of trimetazidine or placebo group. Secondary outcomes included the differences of clinical outcomes, WHO functional class, functional capacity based on SF-36 questionnaire, lactate dehydrogenase and others CMR parameters after 3 months therapy of trimetazidine or placebo group.

Statistical Analysis

The type I error was set two-sided 0.005 with power of 80%. Approximately a minimum 18 patients with PAH and RV dysfunction will be randomized in 1:1 ratio to trimetazidine and placebo group after adjusting to 10% of dropout. A two-sided p value <0.05 was considered statistically significant. Baseline demographic, clinical, laboratory, heart catheterization, and CMR parameters were compared between trimetazidine and placebo group at baseline. Normal distribution of continuous and categorical data were displayed as mean \pm standard error mean and percentage respectively. Categorical data were analyzed using either fisher exact test if one of the data column less than 5 or

Chi square test for larger data. Numerical data were analyzed using independent t tests between trimetazidine and placebo group. Multivariate analysis of covariance (ANCOVA) was performed to determine treatment effect. All analyses were performed using SPSS version 23 (SPSS inc, IBM, Armonk, New York).

TRIMETA-PH Study Protocol

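### The type I error is 0.005 in the sample-size statement but 0.05 in the decision rule, so the stated error rate, power, size and rule cannot all hold

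*Combined protocol and SAP*

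**What the plan says.** All of the relevant text is in the combined protocol and SAP, mostly in one paragraph under Statistical Analysis.

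- **Design error rate and power:** "The type I error was set two-sided 0.005 with power of 80" per cent.
- **Sample size:** "Approximately a minimum 18 patients with PAH and RV dysfunction will be randomized in 1:1 ratio", a number reached "after adjusting to 10% of dropout".
- **Decision rule:** "A two-sided p value <0.05 was considered statistically significant".
- **Primary outcome (Study Outcomes):** "The primary outcome was the differences of RVEF after 3 months therapy of trimetazidine or placebo group".

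For numerical data the section names independent t tests between the groups. It also names an analysis of covariance for the treatment effect, without listing covariates. It gives no RVEF difference, no SD and no source for either.

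**The concern.** A trial's type I error is the probability that its decision rule declares an effect when there is none, so the two figures should be the same number. Here both are two-sided, neither is limited to particular outcomes, and one is ten times the other. There is a single primary outcome, so on a natural reading both apply to the RVEF comparison.

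The success criterion for that outcome is at stake. A result with p = 0.02, for example, is significant under the decision rule and falls short of the stated error rate. Small trials can easily produce p-values in that range. If the threshold is settled only after the data are seen, the verdict can be chosen along with it. The power statement is affected too, because 80% power means something only at a given alpha.

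**Working it through.** **Inputs.** From Statistical Analysis: alpha 0.005 and 0.05 (both two-sided), power 80%, 18 randomised 1:1, dropout 10%, independent t test. The RVEF difference and SD are not given, so 18 cannot be rebuilt forward. The check solves backwards for the standardised difference d (true difference divided by SD).

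**Assumptions.** 18 is the total; exactly 10% is lost; the primary test is an unadjusted two-sample t-test.

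**Step 1: dropout.** 18 × 0.9 = 16.2, so about 16 are evaluable, 8 per arm. In reverse, 16 / 0.9 = 17.8, rounded up to 18. The dropout step is consistent with the stated 18.

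**Step 2: relative size at the two levels (normal approximation).** For fixed d, n per arm is 2(z₁₋α⁄₂ + z₀.₈)² / d². The ratio of n at 0.005 to n at 0.05 is

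(2.807 + 0.842)² / (1.960 + 0.842)² = 13.31 / 7.85 = 1.70.

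Whatever the effect and SD, 80% power at 0.005 takes about 1.7 times as many patients. One N cannot give exactly 80% at both levels.

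**Step 3: detectable difference with 8 per arm.** Normal approximation: d = (z₁₋α⁄₂ + z₀.₈)√(2/8).

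- At 0.05: 2.802 × 0.5 = 1.40.
- At 0.005: 3.649 × 0.5 = 1.82.

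Exact t-test: 14 degrees of freedom, non-centrality d√(8/2) = 2d, critical values 2.145 and 3.326. Solving for 80% power gives d = 1.507 at 0.05 and d = 2.128 at 0.005.

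**Step 4: exchange the levels (exact t-test).**

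| If 18 was derived at | Effect with 80% power | Power at the other level | Evaluable per arm for 80% at the other level |
|---|---|---|---|
| 0.05 | 1.51 SD | 41.7% at 0.005 | 14 (28 in all; 28/0.9 = 31.1, so 32 randomised) |
| 0.005 | 2.13 SD | 97.7% at 0.05 | 5 (10 in all; 10/0.9 = 11.1, so 12 randomised) |

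The normal approximation gives 49.8% and 95.4% for the two powers.

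**Step 5: other readings of the sample size (exact t-test).**

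| Evaluable per arm | d at 0.05 | d at 0.005 | Power at 0.005 if sized at 0.05 | Power at 0.05 if sized at 0.005 |
|---|---|---|---|---|
| 8 | 1.51 | 2.13 | 42% | 98% |
| 9 (no dropout) | 1.41 | 1.97 | 43% | 97% |
| 16 (18 read as per arm, less dropout) | 1.02 | 1.38 | 46% | 97% |
| 18 (18 read as per arm, no dropout) | 0.96 | 1.29 | 46% | 96% |

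The detectable difference depends on the reading. The conflict between the levels does not.

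**The case against.** The strongest reply is that the plan has only one explicit decision rule, p < 0.05. The 0.005 is a design parameter and may be a slip for 0.05, in which case the operative rule does not change. Neither sentence names RVEF, so applying both to the primary comparison is an inference. The slip is plausible, but without an effect size the text cannot confirm it. Even if it is a slip, the stated type I error is wrong by a factor of ten and needs correcting.

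Second, sizing at 0.005 and testing at 0.05 could be called conservative. This is right about power: 18 patients with 80% power at 0.005 is not contradicted if the assumed difference was about 2.13 SD, and power at 0.05 would then exceed 80%. The stated error rate would still not hold. The failure of the power claim therefore belongs only to the branch where 18 was derived at 0.05.

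Third, the absolute figures rest on an unadjusted t-test with 8 per arm, while 18 is given as an approximate minimum and a covariance analysis is also named. This stands. If baseline RVEF were the covariate, the detectable difference at 0.05 would be about 1.516 × √(1 − ρ²), where 1.516 is the t-test solution with one degree of freedom fewer. For assumed baseline-to-follow-up correlations of 0.5, 0.7 and 0.8, that is 1.31, 1.08 and 0.91 SD. Adjustment scales the detectable difference at both levels alike and leaves the conflict between them.

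Finally, this is a single-centre proof-of-concept study. That bears on how much weight its result should carry. It does not remove the need for a single error rate.

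**Conclusion.** The concern holds: the paragraph is wrong as written. It gives two values, a factor of ten apart, for a quantity that can have only one, and nothing elsewhere in the document reconciles them. This conclusion follows from the text alone and needs no assumption about effect size.

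The consequence depends on which value was used. If 18 was derived at 0.05, power at 0.005 is about 42%, not 80%. If it was derived at 0.005, power is adequate, but testing at 0.05 gives ten times the stated false-positive rate. Those power figures assume 8 evaluable per arm and an unadjusted t-test. They change little under other readings of 18, whereas the 1.51 and 2.13 SD differences do change and should be read as conditional. The missing RVEF difference and SD are a related gap: they prevent 18 from being reproduced at either level. This must be fixed, because it concerns the criterion for the only primary outcome.

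**What to change.** Establish from the dated sample-size calculation which alpha was used, then state that one value in both sentences. Parts of the document are in the past tense. If any results were known when the text is changed, the change should be disclosed as a correction and supported by that calculation, not chosen in the light of the data.

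- **If 0.005 was a slip:** change it to two-sided 0.05 and keep the p < 0.05 rule.
- **If 0.005 was intended and 18 was derived at it:** change the decision rule for RVEF to p < 0.005.
- **If 0.005 was intended but 18 was derived at 0.05:** change the rule in the same way and withdraw the 80% claim. Either state the power actually available for the planned effect (about 42% under the assumptions above) or raise the size to 28 evaluable, 32 randomised.

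In each case, restate the power with the assumed RVEF difference and SD in percentage points, say whether the SD is of the final value or the change, and name the test. Possible wording for the first case, if the t-test is primary: 8 evaluable patients per arm give 80% power for a between-group difference of about 1.5 SD in RVEF at two-sided 0.05. For the second case the corresponding figure is about 2.1 SD at two-sided 0.005.

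The cost is one or two sentences and no added patients, unless the third case applies and 80% power is to be kept. The stated detectable difference will look large, but it is what this sample size can support.

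### Does displaying continuous data as mean ± standard error, and not standard deviation, call for a change to the plan?

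*Combined protocol and SAP*

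**What the plan says.** The display rule is one sentence in the Statistical Analysis section. It opens "Normal distribution of continuous and categorical data were displayed as mean" and, after the ± sign, ends "standard error mean and percentage respectively". So normally distributed continuous variables get a mean and its standard error, and categorical variables get a percentage. The document mentions no SD, range or quartiles, and gives no rule for continuous variables that are not normally distributed.

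The sentence just before it reads "Baseline demographic, clinical, laboratory, heart catheterization, and CMR parameters were compared between trimetazidine and placebo group at baseline". The display rule does not itself name baseline data. That it applies to them is an inference, though a reasonable one, from its general wording and its position.

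On size, the same section says "Approximately a minimum 18 patients with PAH and RV dysfunction will be randomized in 1:1 ratio", "after adjusting to 10% of dropout". On inference, it plans independent t tests between the arms and then states: "Multivariate analysis of covariance (ANCOVA) was performed to determine treatment effect".

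**The concern.** A baseline table should show who was enrolled and how varied they were. SD does that and settles towards a fixed value as the sample grows. SEM answers another question, how well the arm's mean is known, and shrinks as n grows. If a reader takes the ± figure for spread, each arm looks more homogeneous than it is, and any gap between the arms looks larger relative to spread by a factor of √n.

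Two features of this trial sharpen the worry. It is a small single-centre proof-of-concept study, and the document gives no SD for right ventricular ejection fraction (RVEF), so the observed SD would be useful to whoever plans a later trial. Also, the entry limits cut off key variables (RVEF below 45%, mean pulmonary artery pressure at least 25 mmHg). Skewed distributions are therefore plausible, and the rule does not cover them.

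**Working it through.** **Inputs from the documents.** At least 18 randomized, 1:1 allocation, 10% dropout (Study Protocol and Statistical Analysis sections). No SD or effect size is given, so the results below are in SD units.

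**The plan's own figure.** The effect size behind the 18 is not stated, so only the dropout step can be reproduced. With 8 evaluable per arm, 16 / 0.9 = 17.8, which rounds up to 18. In the other direction, 18 / 2 = 9 per arm randomized, and 18 × 0.9 = 16.2, about 8 per arm remaining.

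**Size of the SEM.** SEM = SD / √n.
- n = 9: SEM = SD / 3.00 = 0.333 SD
- n = 8: SEM = SD / 2.83 = 0.354 SD

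**Share of patients inside the ± band, for normal data.**
- mean ± SD: 2Φ(1) − 1 = 0.683
- mean ± SEM, n = 9: 2Φ(0.333) − 1 = 0.261
- mean ± SEM, n = 8: 2Φ(0.354) − 1 = 0.276

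So the SEM band does not describe patient-to-patient spread.

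**Recovering the SD.** SD = SEM × √n, which is 3.00 × SEM at n = 9 and 2.83 × SEM at n = 8. This needs the label, which the plan supplies, and the n behind each mean, on which the plan is silent.

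**Effect on the t test.** With n per arm in both arms, the pooled standard error of the difference is √[(SD₁² + SD₂²) / n]. Because SEM² = SD² / n, this equals √(SEM₁² + SEM₂²). The t statistic and p value are therefore the same whichever figure is printed. The ANCOVA works from patient-level data and does not use the displayed figure at all.

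**Per-arm SEM and the error of the difference.** If the arms have equal SEMs, the unadjusted 95% half-width for the difference is t(0.975) × √2 × SEM.
- 9 per arm, 16 df: 2.120 × 1.414 = 3.00 SEM
- 8 per arm, 14 df: 2.145 × 1.414 = 3.03 SEM

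Per-arm SEMs are thus no substitute for an interval on the treatment effect. That concerns how the ANCOVA result is reported, and replacing SEM by SD in the tables would not settle it.

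**The case for a change.** The best case for a change is that it costs one sentence and would be right: mean ± SD, with median and interquartile range for skewed variables, n for each variable, and a confidence interval for the ANCOVA difference. Readers should not have to rebuild a basic descriptive statistic, and they can do so only if n is printed for each variable and visit, which the rule does not require. If more than 18 patients are enrolled, √n rises and the SEM understates spread further.

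Much of this stands. SD is the better choice for a baseline table, the arithmetic is correct, and nothing else in the document supplies a measure of spread. Three things limit its weight.

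- The plan names the statistic correctly. It does not present a standard error as an SD, so the supposed misreading goes against the stated label. A missing label or missing n would be a failure of the eventual report, which the plan neither requires nor rules out.
- The argument is about descriptive tables. Requiring SD for the 3-month outcome means as well goes further than the argument supports, because a labelled SEM beside a t test is a defensible statement of precision.
- Quartiles for skewed data, n per variable, counts beside percentages and an interval for the treatment effect are details that analysts supply when they build tables. The interval and the rule for skewed data are also separate matters and add nothing to the case against SEM.

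**Conclusion.** The observation is accurate, but it does not call for a change to the plan. At the planned minimum of 9 per arm the displayed ± is one third of the SD (SD / 2.83 at about 8 per arm after dropout). In general the factor is √n for the number actually analysed, since 18 is an approximate minimum. The effect on any estimate, test, error rate or power is nil. The SD can be recovered exactly, apart from rounding in the printed figures.

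This rests on three assumptions: that the display rule reaches the baseline table, which is inferred; that the report keeps the standard-error label; and that it gives n with each mean. An analyst who prefers SD in the baseline table can use it at the reporting stage without touching the design, the data collection or the planned analyses.

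### Read literally, WHO functional class at 3 months is compared between arms without using the known entry class (II or III); the plan should state how entry class is used, preferably by an exact test stratified on it.

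*Combined protocol and SAP*

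**What the plan says.** Study Outcomes in the combined protocol and SAP states: "Secondary outcomes included the differences of clinical outcomes, WHO functional class, functional capacity based on SF-36 questionnaire", together with lactate dehydrogenase and "others CMR parameters after 3 months therapy of trimetazidine or placebo group". No variable for change in class is defined.

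For categorical outcomes, Statistical Analysis gives this rule: "Categorical data were analyzed using either fisher exact test if one of the data column less than 5", with chi-square for larger data. No baseline term is attached to either test.

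Entry class is restricted by Study Population: "WHO functional class II or III, evidence of RV dysfunction with RVEF" below 45%. Class IV is excluded. Study Protocol adds: "Functional class was assessed during monthly visit according to WHO".

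**The concern.** A test on month-3 class alone counts a patient who improved from III to II the same as one who stayed in II throughout. Differences in entry class then act as noise, so a real shift in class is harder to see. In a small trial, a chance difference between arms at entry can also carry through to month 3 and look like a drug effect, or hide one.

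The information needed to reduce both problems is already held, because nobody can be enrolled without a class of II or III.

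**Working it through.** **1. Does anything else bring entry class in?**
- Allocation: "Patients who met the following inclusion and exclusion criteria will be randomized in 1:1 ratio to receive" trimetazidine or placebo. No stratification by class is described.
- Baseline data: "CMR parameters were compared between trimetazidine and placebo group at baseline", along with the other baseline variables. This describes the arms at entry; no use in the outcome comparison is stated.
- Modelling: "Multivariate analysis of covariance (ANCOVA) was performed to determine treatment effect". No outcome or covariate is named, and ANCOVA is a method for continuous outcomes.

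So nothing in the text fills the gap for WHO class.

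**2. Evaluable patients.** The plan gives 18 in total, 1:1, with 10% dropout. 16 / 0.9 = 17.8, rounded up to 18, so 18 is consistent with 16 evaluable, or 8 per arm. The plan gives no power figure for WHO class to reproduce. The threshold used below is the plan's two-sided 0.05; the same section also states 0.005 for the design, which is a separate matter.

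**3. Chance imbalance at entry.** Assume half enter in class III. The difference between two Binomial(8, 0.5) counts is distributed as Binomial(16, 0.5) − 8.
- P(arms differ by 3 or more) = 2 × (1 + 16 + 120 + 560 + 1,820 + 4,368) / 65,536 = 2 × 6,885 / 65,536 = 0.21.
- P(differ by 4 or more) = 2 × (6,885 − 4,368) / 65,536 = 0.077.

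With a quarter in class III these are 0.144 and 0.040; with a tenth, 0.037 and 0.005.

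**4. A worked case (9 per arm, invented data).** Treated patients enter with 6/9 in class III; 4 of these improve, leaving 2/9. Controls enter with 3/9 in class III and none move.
- Fisher on month-3 class, 2/9 against 3/9: p = 1.00.
- Fisher on improved, 4/9 against 0/9: 2 × 126 / 3,060 = 0.08.
- Exact test stratified by entry class: only the class III stratum is informative (6 treated, 3 control, 4 improvers). P(4 treated improvers) = 15/126. The equally or more extreme result on the other side, 1 treated improver, has P = 6/126. So p = 21/126 = 0.17.

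Using entry class reveals the movement. Stratification is more cautious than the pooled test here because only 3 controls could have moved from III.

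**5. No drug effect (simulation, 8 per arm, half in class III).** Rates are improved/unchanged/worsened in %, the same in both arms, and are assumptions. Cells give rejection in all trials; with entry difference of 3 or more; of 4 or more.

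| Rates | Fisher on month-3 class | Fisher on pooled change |
|---|---|---|
| 10/80/10 | 3%; 10%; 20% | below 1% throughout |
| 25/60/15 | 3%; 7%; 10% | 3% throughout |
| II 5/80/15, III 30/65/5 | 3%; 7%; 12% | 2%; 2%; 3% |

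A stratified exact test conditions on the number of patients from each entry class in each arm, so it holds its 5% level at any imbalance by construction.

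**6. Power (simulation, 8 per arm, half in class III).** Placebo is 10/80/10 in the first three rows. All rates are assumptions. Exact Fisher (Freeman-Halton) was used for the first two methods and an exact ordinal test of change within entry class for the third. Simulation error is about one point.

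| Assumed movement | Month-3 class | Pooled change | Stratified by entry |
|---|---|---|---|
| Drug 40/50/10 | 6% | 15% | 11% |
| Drug 60/40/0 | 15% | 39% | 45% |
| Drug 60/30/10 | 14% | 48% | 28% |
| Drug II 0/95/5, III 70/30/0; placebo II 0/70/30, III 10/80/10 | 26% | 18% | 33% |
| As above, but drug III 90/10/0 | 43% | 31% | 56% |
| Effect in class III only: II 0/95/5 in both arms; drug III 70/30/0, placebo III 10/80/10 | 11% | 12% | 20% |

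**7. Entry mix.** At drug 60/30/10, month-3 class against pooled change gives 25% against 48% with a quarter in class III, and 38% against 48% with a tenth. With a single entry class the two are identical.

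**The case against.** **The literal analysis is not wrong.** This stands. Randomisation makes the month-3 comparison unbiased, and its overall rejection rate with no drug effect is about 3%, below the nominal 5%. A reader might infer from the 10% and 20% figures that false positives are inflated. They are not: those figures apply only to the 21% and 8% of trials with marked imbalance at entry. The cost is precision and vulnerability to an unlucky draw.

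**Change may have been meant.** Study Outcomes speaks of differences after 3 months, which could mean change from entry. This also stands, so the documents do not show that entry class will be ignored. They leave two readings that can give different answers from the same data. The same phrase governs the other outcomes, and a plan-wide definition of outcomes as change would settle the meaning here.

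**Change from entry is not always better.** A reader might conclude that a Fisher test on pooled change is a free gain. It is not. It gains when class II and III entrants move alike and loses when movement depends on entry class (rows 4 and 5 of the power table). If month-3 class did not track entry class at all, power at 9 per arm would be 37–39% for month-3 class and 19–26% for pooled change. In that case stratification has nothing to gain either and may cost some power. Strong tracking is more plausible over 3 months on stable background therapy, but the documents give no transition rates to confirm it.

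**It is minor.** Agreed: this is one secondary outcome in a small proof-of-concept trial.

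**Conclusion.** The point holds as a request to use entry class and to say how. As written, the only test that reaches WHO class is unadjusted, and a known and probably prognostic baseline value is left out. With half entering in class III and the assumed rates, stratifying by entry class raised power over the literal analysis in all six drug-effect scenarios, by 5 points (11% against 6%) to 30 points (45% against 15%). Power remained modest throughout, at most 56%, so the result would be exploratory under any method.

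The sizes rest on assumed entry mix and transition rates and on 8 evaluable per arm. The gain shrinks when the effect is small or nearly all patients enter in one class, and is nil with a single entry class. The documents do not support calling the planned test invalid or pooled change uniformly superior, and nothing here touches the RVEF conclusion or the sample size.

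**What to change.** Add to Statistical Analysis that WHO class at month 3 is compared between arms as change from entry (improved / unchanged / worsened), by an exact ordinal test (rank or linear-score) stratified by entry class II or III. List entry class explicitly as a baseline variable; at present it is only implied by eligibility. Report the improved, unchanged and worsened counts by arm and entry class so that the direction is visible, and label the result exploratory.

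Fisher on pooled change is an acceptable simpler alternative if the team prefers the test already named, provided the choice is fixed in advance and its dependence on similar movement in both entry classes is acknowledged. If change was already intended, correcting the wording is enough.

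The cost is low: existing data, with no new visits or patients. The downsides are a slightly less familiar exact test and, in some settings, less power than the pooled test (28% against 48% at drug 60/30/10).

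### No test is named for WHO functional class, an ordered secondary outcome, and the rule it most naturally falls under (Fisher or chi-square) ignores class order; the power cost depends on assumptions and is often small

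*Combined protocol and SAP*

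**What the plan says.** Study Outcomes lists functional class among the secondary comparisons after 3 months: "Secondary outcomes included the differences of clinical outcomes, WHO functional class, functional capacity based on SF-36 questionnaire". Study Protocol adds "Functional class was assessed during monthly visit according to WHO". Study Population restricts entry to "WHO functional class II or III", so classes I and IV can appear only after baseline.

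Statistical Analysis offers three routes:

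- Categorical data: "Categorical data were analyzed using either fisher exact test if one of the data column less than 5 or", then "Chi square test for larger data".
- Numerical data: "Numerical data were analyzed using independent t tests between trimetazidine and placebo group".
- A model sentence that names neither outcome nor covariates: "Multivariate analysis of covariance (ANCOVA) was performed to determine treatment effect".

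The threshold is "A two-sided p value <0.05 was considered statistically significant". No rank, trend or ordinal method is mentioned, and functional class is not assigned to any route by name.

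**The concern.** A four-level class recorded as I to IV is usually handled as categorical data, so the Fisher/chi-square rule is where an analyst following this text would most likely take it. With three or more classes observed, both tests treat the classes as unordered labels. The clinical question is directional: do patients on trimetazidine end in a better class?

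Two things are at stake. An order-blind test spreads its sensitivity over every pattern of difference, so it can miss a consistent shift. It can also return p<0.05 for a pattern in which neither arm is better. A change score (improved, same, worse) tested under the same rule would lose its order in the same way.

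**Working it through.** **Inputs from the documents.** Minimum 18 patients, 1:1, read here as 9 per arm; 10% dropout; two-sided 0.05 for analysis. The plan states no power for functional class, so there is no figure to reproduce. The one step that can be checked is dropout: 16/(1 - 0.10) = 17.8, rounded up to 18, which fits about 8 evaluable patients per arm. Both 8 v 8 and 9 v 9 are used below.

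**Assumptions, not in the documents.** The placebo class distribution and the size of the effect. The active arm is shifted by a common odds ratio (OR): if c is a placebo cumulative proportion, the active one is OR·c/(1 - c + OR·c). For 10/50/40% and OR 8: 0.8/(0.9 + 0.8) = 0.471 and 4.8/(0.4 + 4.8) = 0.923, so the active arm is about 47/45/8%.

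**Which test the rule selects.** Nine patients split over two or more classes must leave some count at 4 or fewer. If the rule's cut-off refers to cell counts, it always leads to Fisher.

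**Order is ignored.** Take I/II/III counts of 1/7/1 v 4/1/4.

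- Fisher: this table has probability C(5,1)·C(8,7)·C(5,1)/C(18,9) = 200/48,620. Summing all tables no more probable gives 880/48,620, p = 0.018.
- Wilcoxon: the midranks are 3, 9.5 and 16. The first arm's rank sum is 3 + 66.5 + 16 = 85.5, exactly its null expectation 9·19/2 = 85.5, so p = 1.00.
- Swap the labels I and II, giving 7/1/1 v 1/4/4. Fisher is still 0.018. The rank sum becomes 7·4.5 + 11 + 16 = 58.5 and the exact Wilcoxon p is 580/48,620 = 0.012.

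The opposite case also exists: 3/5/1 v 0/4/5 is a clear shift, with Fisher p = 0.091 and exact Wilcoxon p = 0.039.

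**Power by complete enumeration.** For every 2×k table, compute the Fisher (Freeman-Halton) p and the exact conditional Wilcoxon p with midranks, then add up the product-multinomial probabilities of p<0.05. Entries are Fisher v Wilcoxon, in %.

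| Placebo distribution | Per arm | OR 5 | OR 8 | OR 12 |
|---|---|---|---|---|
| 10/50/40% | 9 | 22.8 v 28.1 | 37.7 v 46.1 | 52.8 v 62.4 |
| 10/50/40% | 8 | 18.1 v 22.9 | 30.1 v 38.7 | 42.8 v 54.0 |
| 15/45/30/10% | 9 | 22.8 v 33.0 | 38.0 v 51.4 | 52.4 v 66.6 |
| 15/45/30/10% | 8 | 18.2 v 27.5 | 30.9 v 43.8 | 44.0 v 58.1 |

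The loss is thus about 5 to 11 points with three classes and 9 to 14 with four. At OR 3 with 10/50/40% it is under 2 points. If the analyst used Pearson chi-square instead, the 9 v 9, OR 8 figures would be 42% v 46% (three classes) and 37% v 51% (four).

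**Less favourable assumptions, 9 v 9, gain of Wilcoxon over Fisher in points:**

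| Placebo distribution | OR 3 | OR 5 | OR 8 |
|---|---|---|---|
| I/II/III 5/50/45% | 0.5 | 2.3 | 5.1 |
| I/II/III 5/65/30% | -0.6 | 0.4 | about 2 |
| I/II/III 2/53/45% | -0.3 | -0.1 | about 0.5 |
| improved/same/worse 10/80/10% | -0.6 | -0.5 | about 0 |
| improved/same/worse 20/70/10% | -0.2 | 1.4 | 3.5 |

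At OR 12 the largest gain among these rows is about 7 points. If only two classes occur and the arms are equal in size, the two exact tests are identical and the gain is zero.

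**Error rates.** With identical arms both tests reject in about 2 to 4% of trials for 10/50/40% and 15/45/30/10%, and less often in the sparse settings. The chance that Fisher gives p<0.05 while Wilcoxon gives p≥0.5 stayed under 1% in every common-odds-ratio scenario run.

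**The case against.** The strongest reply has four parts.

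1. *The route is inferred.* This stands. The plan does not assign functional class to Fisher or chi-square, and the ANCOVA sentence names no outcome. But none of the three routes is built for an ordered scale, so the same sentence is needed whichever was intended.
2. *The power loss is a product of the assumptions.* This largely stands. A reader might infer that Fisher costs 5 to 13 points whenever three or more classes occur. The documents do not support that: they give no class distribution and no effect size. Under 5/65/30%, three classes occur in 82 to 95% of trials at OR 3 to 8, yet the gain runs only from -0.6 to about 2 points. Because patients enter in class II or III, a placebo arm with 10% in class I at month 3 is towards the favourable end.
3. *The directionless example is hand-picked.* This stands as to frequency under a common odds ratio. Fisher would reject often if the arms truly differed only in spread (57% v 9% for Wilcoxon at 9 v 9, with 33/34/33% v 5/90/5%), but that would be a real difference in distribution. It is not an inflated false-positive rate.
4. *It changes little.* At OR 5 with the three-class distributions tabulated, either test has power below 30%. Choosing the better test does not make this outcome conclusive.

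One limit of the remedy also stands: an unadjusted month-3 comparison does not use entry class, which could be unbalanced with 9 per arm.

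**Conclusion.** The point holds in limited form. An ordered secondary outcome has no named test; the likely one ignores order, and a better-suited exact test is available at almost no cost.

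The size is conditional on assumed distributions, a common odds ratio, 8 or 9 per arm and the 0.05 threshold. It is about 5 to 11 points of power with 10/50/40% and OR 5 to 12, and about 9 to 14 with a fourth class. With few class I patients or mostly unchanged patients it is about -0.6 to +5 points at OR 3 to 8, and up to about 7 at OR 12. It is zero with only classes II and III. Reading 18 as the total is itself an assumption.

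A reader might also infer that the plan produces false positives for functional class. It does not: neither test exceeds 5% when the arms are identical. The primary RVEF analysis is unaffected, and this is a minor improvement.

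**What to change.** In Statistical Analysis, keep Fisher and chi-square for binary and unordered data (for example sex, or occurrence of MACE) and add: *WHO functional class at 3 months will be compared between groups by the two-sided exact Wilcoxon-Mann-Whitney test on the ordered classes.* If a class-change score is reported, name the same test for it, expecting little gain when most patients are unchanged.

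The cost is one sentence, with no new data or patients. The drawbacks are slightly less sensitivity to non-monotone patterns, which are not the question being asked, and at most about 1 point of power in sparse three-class settings.
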